13.2.3 Mechanistic Assay Analyses

The primary mechanistic objective of CTOT studies is to identify and elucidate pathophysiologic and genetic mechanisms that are associated with allograft rejection and how these associations may evolve over time and/or differ between therapeutic treatments. In this study, the principal objectives of the mechanistic analyses of data from subjects receiving kidney or pancreas transplants will include assessment of the association between treatment (i.e., belatacept vs. tacrolimus maintenance) and renal function, incidence of viral infection and autoimmunity.

Ten mechanistic assays are described in Section 12. There are from 1 to 3 separate correlations or tests desired for each assay category and these are described in Table 8. The analysis numbers in the table refer to the following 10 assays:

- 1. Intracellular cytokine staining and viral phenotyping
- 2. Flow cytometry
- 3. Protein Assays
- 4. Gene expression, mRNA profiling
- 5. Anti-HLA alloantibodies and non-HLA antibodies
- 6. Autoimmunity markers
- 7. Genomics (gene polymorphisms)
- 8. Renal histology
- 9. Renal immunohistochemistry
- 10. Pancreatic histology
- 11. Viral testing (viral load determination)

Depending on the scale of measurement of the endpoints, the amount of missing data, and the questions of interest, exploratory data analysis (EDA) and/or statistical hypothesis testing and modeling will used. Given the small sample sizes (n=30 in each of 2 treatment arms), modeling and testing will generally be restricted to the continuous endpoints where the focus will be testing for treatment and time effects on repeated measures of the endpoints. These types of analyses will have sufficient sample sizes to make reasonable inferences; e.g., repeated measures ANCOVA tests for differences in gene expression in the treatment arms, over 5 assessment times would have to following degrees of freedom for the their error terms: treatment df = 58; time df = 238, time × treatment = 238.

Page 87 of 104

Analysis No.	Effector cells, antibodies, or markers (see Sect. 12)	Meas. Scale	Assay	Objective	Analysis Method ¹
1a	Virus-specific T- cell subpopulations	Continuous. (cell counts)	Cytokine staining + PCR	Correlation with viral loads detected with PCR, by visits and treatment arm	Spearman Rank Correlation Coeff., by visit and treatment group; treatment x time plots; tables of summary stats.
1b	Virus-specific T- cell subpopulations	Binary	Cytokine staining + PCR	Comparison of prevalence of each T-cell type by visits and treatment arm	Contingency tables and Cochran Mantel Haenszel (CMH) tests
1c	Virus-specific T- cell subpopulations	Continuous. (cell counts)	Cytokine staining + PCR	Correlation with B-cell counts, NK cell counts, dendritic cell counts by visit and treatment arm	Spearman Rank Correlation Coeff., by visit and treatment group; treatment x time plots; tables of summary stats.
2a	Donor-reactive T- cell subpopulations	Continuous. (cell counts)	Flow Cytometry	Look for treatment arm differences in counts, over time	Random Effects repeated measures ANCOVA (RMANCOVA); treatment x time plots and random coefficients models and plots; tables of means and standard errors
2b	Donor-reactive T- cell subpopulations	Continuous. (cell counts)	Flow Cytometry	Correlation with eGFR, de novo anti-donor HLA and biopsy findings, by visits and treatment arm	Spearman Rank Correlation Coeff., by visit and treatment group; treatment x time plots; tables of summary stats.
3	Protein Assays				
4a	Gene expression data for > 128 markers	Continuous	Real -time PCR	Identify associations between specific mRNAs and the occurrence of AKI, CHI, CIT, and fibrosis, by visit pooled over trt	EDA: various graphical comparisons and descriptive statistics (by visit if there are enough occurrences of AKI, CKI, CIT, and/or fibrosis

¹ Statistical tests (e.g., t-tests) and statistical models (e.g., ANOVA) will only be performed if sample sizes are adequate

Page 88 of 104

Analysis No.	Effector cells, antibodies, or markers (see Sect. 12)	Meas. Scale	Assay	Objective	Analysis Method ¹
4b	Gene expression data for > 128 markers	Continuous	Real -time PCR	Look for evidence of treatment differences in the occurrence of each marker over time	Separate RMANCOVAs for each marker; treatment x time plots; tables of means and standard errors by marker, treatment arm, and visit
5a	Anti-HLA and non-Anti-HLA antibodies	Continuous	Luminex	Characterize the occurrence of HLA-A, B, C, DR, DQ α , DQ β , DP β , and anti- MICA, by treatment arm and visit	Separate RMANCOVAs for each ab.; treatment x time plots; tables of means and standard errors by antibody, treatment arm, and visit
5b	Anti-HLA and non-Anti-HLA antibodies	Binary (present absent)	Luminex	Examine prevalence patterns of HLA- A, B, C, DR, DQα, DQβ, DPβ, and anti- MICA	Contingency tables and CMH tests by marker ; treatment x time plots; tables of prevalence means and stderrs by treatment arm and visit
5c	De Novo donor- specific anti-HLA antibodies	Continuous	Luminex	Correlation with eGFR, and biopsy findings (if enough are done), by visits and treatment arm	Spearman Rank Correlation Coeff., by visit and treatment group; treatment x time plots; tables of summary stats.
6	Markers of recurrent autoimmune disease following pancreas transplant	Continuous	TBD	Compare distributions of anti-GAD, anti- insulin and anti- IA2 between subjects with AR and no AR	EDA using graphical and tabular summaries of the data in AR vs. non-AR within and between subjects.
7	Genomic analysis of polymorphisms (SNPs) in cytokine genes	Binary	TBD	Determine if differences in cytokine genetic polymorphisms are associated with AR	Logistic regression analysis for additive and recessive hypotheses; wherein, the predictors are the numbers (0,1,2,) of recessive alleles for each SNP.

Page 89 of 104

Analysis No.	Effector cells, antibodies, or markers (see Sect. 12)	Meas. Scale	Assay	Objective	Analysis Method ¹
7	Morphological markers in biospsied kidney tissue + CD4 markers	Continuous + binary (present/absent)	Trichrome, H&E, and CD4 staining	Correlation with visit 1 – week 52 changes in Banff scores and corresponding changes in several morphometric features of the grafts	Spearman Rank Correlation Coeff., by visit and treatment group; tables of summary stats.
9	Renal markers of fibrosis and inflammation	Binary (present/ absent)	Immuno- histochemical staining	Compare genomic, proteomic, cytokine profiles in subjects with/without the renal markers	Tables of summary statistics to compare within-subject changes in markers and profiles between visit 1 and week 52.
10	Morphological markers in biospsied pancreatic tissue + CD4 markers	Continuous + binary (present/absent)	Trichrome, H&E	Correlation with visit 1 – week 52 changes in Banff scores and corresponding changes in several morphometric features of the grafts	Spearman Rank Correlation Coeff., by visit and treatment group; tables of summary stats.
11a	Prevalence and intensity (viral load) of several pathogenic viruses	Binary (present/absent)	Quant. PCR	Prevalence of CMV, BKV, JCV, HHV6, HH7, and EBV	Contingency tables and CMH for treatment time differences in prevalence of each viral species
11b	Prevalence and intensity (viral load) of several pathogenic viruses	Continuous	Quant. PCR	Viral loads of HHV6, HHV7,Polyoma JC, Polyoma WC, and KI	Separate RMANCOVAs on each virus; treatment x time plots; tables of means and standard errors by virus, treatment arm and visit

 Table 10.
 Summary of Mechanistic Data Analyses

Page 90 of 104

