10.3 Study Assessments

Subjects enrolled in this study will be followed for a minimum of 52 weeks post-transplant in order to assess the primary endpoint. Subjects in the Investigational Arm who are eligible and attempt tacrolimus withdrawal will be followed for at least 60 days following the withdrawal of tacrolimus. Subjects may be followed for up to 18 months (76 weeks) depending upon study completion.

Subjects will have blood, tissue and urine collected for research studies at the following timepoints:

- Visit 1 (Pre-Transplant to Day 4 Post-Transplant)
- Post-Transplant: Days 28, 84 and Weeks 28, 36, and 52.

Clinical safety will be monitored through routine physical examinations and appropriate laboratory assessments every 4 weeks for the duration of the study. During this period, subjects will have repeated clinical/laboratory evaluations, as specified in the Schedule of Events (Appendix 1 through 3, Schedule of Events- Recipient and Appendix 4 – Reduced Follow-Up Schedule of Events - Recipient).

Infusion Supervision

In addition to the study visits and procedures listed in Appendix 1-4, participants assigned to the Investigational Arm will receive a NULOJIX® (belatacept) infusion on days 5, 14, 28, 56 and 84 post-transplant. After 84 days, participants in the Investigational Arm will continue NULOJIX® (belatacept) infusions every 4 weeks throughout the duration of the study. The infusion will be administered in a center where full resuscitation facilities are immediately available and under close supervision of the investigator or infusion center staff. A history of each infusion and any adverse side effects will be recorded and reported to the SACCC using the appropriate case report forms. Vital signs (temperature, blood pressure, pulse, and respiratory rate) will be obtained prior to the start of each infusion and again at the end of the infusion. Additional vital signs will be obtained as clinically indicated. At the discretion of the investigator, the infusion may be discontinued if there is a severe reaction to the infusion.

Clinical Assessments

Assessments for the development of new adverse events, serious adverse events, infections, rejections, graft loss, hospitalizations, new onset diabetes, and malignancies will be completed at each study visit. All events will be reported using a designated electronic case report form (eCRF).

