13.2 Endpoint Assessments

13.2.1 Primary Clinical Endpoint

The primary endpoint will be the week-52 eGFR. Mean eGFR of the belatacept group will be compared to the mean eGFR of the tacrolimus reference group within a mixed models repeated measures (MMRM) framework , wherein repeated measures of eGFR at weeks 4, 12, 28, 36 and 52 will be modeled as a linear function of time (and perhaps other baseline covariates) in the 2 treatment groups. At week-52, a contrast will be made between the eGFR mean of the belatacept group and the eGFR mean of the tacrolimus group. ANCOVA assumptions will be evaluated graphically via standard residual analyses. If the assumptions fail, a suitable transformation (e.g., natural logarithms) will be found and the data will be reanalyzed on the transformed scale. Results will be reported with p-values associated with the F-test for each contrast and the corresponding mean treatment differences with two-sided 95% confidence intervals. All tests of significance will be two-tailed at the 0.05 level.

Estimating the contrasts within the repeated measures framework will provide treatment comparisons that are robust to subject dropout bias as long as the dropout pattern is missing at random²⁷. Data are missing at random whenever the "missingness" mechanism is a function of observable relationships among the nonmissing responses and covariates. Using the methods of Ma et al.²⁸, we will evaluate the MAR assumption in the data prior to implementing the MMRM analysis. If the MAR assumption fails, we will consider more robust alternatives (e.g., pattern mixture modeling)²⁹.

A number of studies have shown RMANCOVA to be superior to analyses of completers or of data with LOCF imputations³⁰. Nonetheless, we will conduct 2 related sensitivity analyses: (1) replace the missing week-52 values with the corresponding nonmissing week 36 values of each subject, dropping anyone who is missing both week-36 and week-52 and perform the ANCOVA as currently specified; (2) include only the completers in the ANCOVA analysis (i.e., exclude all dropouts). The sensitivity analyses will be included as additional secondary analyses.

13.2.2 Secondary Clinical Endpoints

The secondary endpoints are defined in Protocol section 1.5.

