The protocol defines 28 secondary clinical endpoints. The endpoints are to be computed and summarized by treatment and, in a few cases, by day/week and treatment. With the exception of specific AEs and lab parameters, proportions or means will be estimated for each treatment arm and tested for treatment differences through the use of a statistical model. The particular model to be used depends on the scale of measurement of the endpoint. The accompanying table lists each endpoint and its measurement scale (continuous, dichotomous, and ordinal). All tests of significance in all analyses will be made at the 0.05 level.

Dichotomous measures of prevalence and incidence will be analyzed with log-binomial regression models, wherein treatment effects will be estimated as relative risk ratios; the reference group will be the tacrolimus-thymoglobulin subjects. The log-binomial model (rather than logistic regression) is applied for prevalence and incidence analyses because model-based estimates of relative risk (RR) are both more desirable and appropriate for non-Poisson events that are expected to occur more commonly than in 10% of the cases. In such cases, logistic regression-based odds ratio (OR) estimates are poor estimators of the relative risk³¹,³²,³³,³⁴. It may be appropriate to treat some of the dichotomous outcomes as censored data; if this is the case, we will obtain RR estimates by fitting Cox regression models to the data³⁵.

The single ordinal secondary outcome variable (Banff cell-mediated AR score) will be analyzed in a proportional odds model³⁶ which may include additional covariates and interaction terms, as appropriate.

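### Table 10 names no strata for its CMH tests on repeated binary readings; an arm comparison pooled over visits (row 11a, and rows 5b and 1b if pooled) would exceed its 5% error rate

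*Combined protocol and SAP*

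**What the plan says.** Three rows of Table 10 (Section 13.2.3) assign CMH tests to present/absent readings taken repeatedly in the same subjects.

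- Row 1b, virus-specific T cells. Objective: "Comparison of prevalence of each T-cell type by visits and treatment arm". Method: "Contingency tables and Cochran Mantel Haenszel (CMH) tests".
- Row 5b, anti-HLA and non-HLA antibodies. Method: "Contingency tables and CMH tests by marker", with plots over time and descriptive tables by arm and visit.
- Row 11a, viruses. Method: "Contingency tables and CMH for treatment time differences in prevalence of each viral species".

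No row names the stratification variable, the subject as unit of analysis, or any allowance for correlation within a subject. The continuous rows 2a, 4b, 5a and 11b are given repeated measures ANCOVA. Rows 5a and 5b come from the same Luminex assay, and rows 11a and 11b are both quantitative PCR.

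Two statements limit how often these tests will be run. Section 13.2.3 cites the small arms ("Given the small sample sizes (n=30 in each of 2 treatment arms") and says that modelling and testing will in general be kept to continuous endpoints. The footnote to the Analysis Method column allows tests only where numbers suffice.

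**The concern.** A CMH test combines 2x2 tables over strata and adds the stratum variances as if the strata were independent. If the strata are visits, the same subjects contribute to each one. With five visits, 60 subjects enter the variance as up to 60 x 5 = 300 independent observations. When a subject who is positive at one visit is more likely to be positive at the next, the variance is understated and arm differences are declared too often.

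Stratifying by subject is no way out for an arm comparison, because arm does not vary within a subject.

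The error would repeat over the eight antibody specificities listed in row 5b and the six viruses in row 11a. Rows 1b and 11a bear on protective immunity, which is part of the secondary objective (Section 1.3). Row 5b bears on anti-donor responses, which Section 1.6 lists separately.

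**Working it through.** **Inputs from the documents**

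- Level 0.05: "All tests of significance in all analyses will be made at the 0.05 level" (Section 13.2.2). Two-sided: "All tests of significance will be two-tailed at the 0.05 level" (Section 13.2.1, written for the primary analysis and assumed here to carry over).
- 30 subjects per arm (Section 13.2.3).
- Research samples: "Post-Transplant: Days 28, 84 and Weeks 28, 36, and 52" (Section 10.3), so five post-transplant readings. Appendix 2 confirms five for the antibody samples (row 5b) and the core-laboratory viral PCR (row 11a).
- Row 1b: Appendix 2 marks intracellular cytokine staining only at weeks 28, 36 and 52, so three scheduled post-transplant readings. Appendix 1 adds one pre-transplant sample, making four if it is counted.

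**Input not in the documents:** the within-subject correlation rho. It is assumed equal between all pairs of visits and varied from 0.1 to 0.7.

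**Step 1, nominal rate.** 2 x (1 - Phi(1.96)) = 0.050. A simulated visit-stratified CMH test (30 per arm, 20,000 runs, prevalence 0.1, 0.3 and 0.5, no continuity correction) with independent readings rejects in 4.3% to 5.3% of trials for three to five visits. The test therefore holds its level when its independence assumption is true.

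**Step 2, repeated readings.** With K readings per subject, the variance of the summed numerator is larger than CMH assumes by the factor 1 + (K - 1) x rho. The true error is then

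2 x (1 - Phi(1.96 / sqrt(1 + (K - 1) x rho))).

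For K = 5 and rho = 0.5 the factor is 1 + 4 x 0.5 = 3, then 1.96 / 1.732 = 1.132, and the error is 25.8%.

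| Readings | rho 0.1 | rho 0.3 | rho 0.5 | rho 0.7 |
|---|---|---|---|---|
| 3 (row 1b) | 7.4% | 12.1% | 16.6% | 20.6% |
| 4 (row 1b with pre-transplant sample) | 8.6% | 15.5% | 21.5% | 26.6% |
| 5 (rows 5b, 11a) | 9.8% | 18.6% | 25.8% | 31.5% |

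**Step 3, simulation at rho 0.3, 0.5 and 0.7.** Five readings: 18.3-19.2%, 25.4-26.6% and 31.4-32.5%. Three readings: 11.4-12.4%, 16.2-17.2% and 20.2-21.6%. Both agree with the formula.

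**Step 4, sensitivity.**

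- With a 0.5 continuity correction, five readings give 14.6-17.0%, 21.8-23.2% and 28.0-29.0%; three readings give 7.6-9.2%, 11.5-13.7% and 15.5-17.3%.
- If correlation decays with distance between visits (adjacent-visit value 0.3 to 0.8), the formula gives 12.3% to 30.3% for five readings.

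**Step 5, alternatives.** One uncorrected test at a single visit gives 4.7% to 5.7%. A t-test on each subject's proportion of positive readings gives 4.5% to 5.4% for three to five readings and rho from 0 to 0.75.

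**The case against.** The strongest reply is that Table 10 never says visits are pooled. Rows 1a, 2b and 5c word their objectives much as 1b does, and their method column then specifies a separate analysis for each visit and group. On that usage 1b may well mean one test per visit. Row 5b ties its tests to the marker, and visit governs only its descriptive tables. Tested that way, neither row is inflated. This stands, and it is why the point is conditional for 1b and 5b.

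It is weaker for 11a, which asks for differences over treatment and time. CMH on a single 2x2 table is only the chi-square test multiplied by (N - 1)/N, so naming it suggests strata. Randomization uses no stratification variables (Section 10.4.1) and Table 10 mentions no site stratum, which leaves visit as the only evident candidate for an arm comparison.

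The second reply is that the tests may rarely be run, given the preference for continuous endpoints and the sample-size footnote. That limits the consequence. It does not make the method sound, since adequate numbers do not remove dependence.

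The third is that the correlation is assumed. This stands. Constant prevalence is also a poor model for CMV: antiviral prophylaxis (Section 8.4.1) spans the day 28 and day 84 samples. Nor do all 60 subjects appear at every visit, because the reduced schedule (Appendix 4) lists no core-laboratory samples.

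A reader might infer that row 1b carries an error of 18% to 33% from five readings. The documents do not support that. Row 1b has three scheduled post-transplant readings, and even at rho = 1 the formula gives only 25.8%. For five readings, 18% to 33% requires rho of about 0.28 to 0.76, which is nowhere stated. A reader might also infer that the standard errors tabulated under 5b are wrong. They are reported within each visit and are unaffected by correlation between visits.

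**Conclusion.** The concern holds in conditional form. The plan names CMH for repeated binary readings without naming the strata. If arms are compared across visits, as 11a suggests and as 5b and 1b permit, the test ignores a dependence that the plan already handles for continuous readings. The true error at nominal 5% would be 9.8% to 31.5% for 5b and 11a and 7.4% to 20.6% for 1b. These ranges rest on an assumed exchangeable correlation of 0.1 to 0.7, a two-sided test and no continuity correction. If every test is run at a single visit, this inflation does not arise.

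The reach is confined to mechanistic analyses. The primary endpoint does not depend on it. The related clinical endpoints in Table 9 use one outcome per subject (anti-donor antibody at week 52, incidence of specific infections), fitted by log-binomial or Poisson regression, and so avoid the problem.

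**What to change.** For rows 11a, 5b and 1b, state whether arms are compared across visits or at each visit.

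- Across visits: replace CMH with GEE clustered on subject, with terms for arm, visit and arm x visit and a small-sample-corrected sandwich variance. Where data are sparse, test a per-subject summary such as the proportion of visits positive. The simulation above covers the per-subject test, not the GEE.
- At each visit: say so. A 2x2 test per visit is then adequate for this point; the number of such tests is a separate multiplicity question.
- Having been positive at any time by week 52 is cumulative incidence, not prevalence, and is sensitive to missed samples. It may be added only as a separately labelled analysis.

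The cost is a change of wording in three rows, slightly more programming, and wider intervals that reflect the number of subjects.

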1.6 Mechanistic Secondary Endpoints

Samples for **Mechanistic studies** will be collected as specified on the SOE.

Immune Reactivity and Function

- 1. Multiparameter flow cytometric enumeration and phenotyping of peripheral blood leukocyte subsets. (Emory Cellular Core Laboratory)
- 2. Protective immunity (Emory Viral Surveillance Core Laboratory)
 - a. Viral load monitoring EBV, CMV, Polyoma BKV & JCV
 - b. Quantity and quality of CMV- and EBV- specific T cells and viral-specific antibody.
- 3. Anti-donor responses
 - a. Donor-specific antibody (Emory HLA Clinical Laboratory).
 - b. Immunohistochemistry of for-cause renal allograft biopsies (UCSF Pathology Core Lab).
 - d. Gene expression, mRNA profiling in blood, urine and tissue (University of Alabama Molecular Core Laboratory).
- 4. Serum and urine proteins, selected biomarkers of acute and chronic kidney injury (University of Alabama Protein Assay Core Laboratory).

Page 24 of 104

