CTOT-15 is designed to be a first step in providing the potential benefits of an immunosuppressive regimen based on an agent other than a CNI to this underserved patient population. Currently, SPK recipients have no alternatives to CNIs for maintenance immunotherapy. As a result, immunosuppressive protocols remain dependent on these agents despite the long term nephrotoxicity and beta cell toxicity associated with these agents. Furthermore, as abatacept, a precursor of NULOJIX® (belatacept), has been shown effective for treatment of the autoimmune disease psoriasis, we believe that NULOJIX® (belatacept) may offer unique benefits to pancreas transplant recipients with type I diabetes mellitus by acting to control the autoimmune response.

CTOT-15 will also incorporate a battery of mechanistic assays that are designed to be integrated with many of the assays being performed as part of CTOTC-02 and CTOT-16. These assays compare the effects of the belatacept-based regimen on protective antiviral immunity, alloimmunity, and autoimmunity. The study design allows us to focus on how these two different classes of immunosuppressive agents affect memory responses including those that predate the transplant and those arising from homeostatic lymphocyte repopulation.

Over the last two decades, the short-term results of organ transplantation have improved steadily in large part due to the introduction of increasingly potent immunosuppressants. Calcineurin inhibitors (CNI), such as cyclosporine and tacrolimus, form the backbone of the vast majority of all immunosuppressive regimens currently used in abdominal organ transplantation (www.srtr.org). The success of these CNI-based regimens is demonstrated by the ever-decreasing incidence of acute rejection and the ever-improving 1-year graft survival following de novo renal and extra-renal transplantation. Disappointingly, this improvement in short-term outcomes has not resulted in concomitant improvements in long-term outcomes¹,². The major factors limiting the long-term survival of transplanted kidneys and kidney transplant recipients are the near universal development of

interstitial fibrosis and tubular atrophy (IFTA)³ and the extremely high incidence of cardiovascular disease in transplant recipients. This is particularly true for patients with type 1 diabetes undergoing simultaneous kidney and pancreas transplantation.

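### Table 10 specifies no between-arm test, estimate or interval for virus-specific T-cell counts or for B-, NK- and dendritic-cell counts

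*Combined protocol and SAP*

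**What the plan says.** Section 1.6 names two endpoints that are counts of cells. Item 1 is "Multiparameter flow cytometric enumeration and phenotyping of peripheral blood leukocyte subsets". Item 2b is "Quantity and quality of CMV- and EBV- specific T cells and viral-specific antibody". They serve the secondary objective in Section 1.3 on protective immunity, and Section 2.1 says of the assay battery: "These assays compare the effects of the belatacept-based regimen on protective antiviral immunity, alloimmunity, and autoimmunity".

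Table 10 handles them as follows.

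- Row 1a (virus-specific T cells, continuous): "Correlation with viral loads detected with PCR, by visits and treatment arm". The method is "Spearman Rank Correlation Coeff., by visit and treatment group; treatment x time plots; tables of summary stats".
- Row 1b (the same cells, binary): prevalence by visit and arm, with contingency tables and Cochran-Mantel-Haenszel tests.
- Row 1c (virus-specific T cells, continuous): "Correlation with B-cell counts, NK cell counts, dendritic cell counts by visit and treatment arm", with the same method as row 1a.
- Row 2a (donor-reactive T cells, continuous): "Look for treatment arm differences in counts, over time", by random-effects repeated measures ANCOVA.

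The text above the table says that "modeling and testing will generally be restricted to the continuous endpoints where the focus will be testing for treatment and time effects". A footnote to the table makes every test and model conditional on adequate sample size.

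**The concern.** For analysis 1 the table does not carry through the principle stated above it. The counts are labelled continuous, yet the rows that use them estimate association inside each arm and name no treatment effect. The one between-arm test, row 1b, discards the count and keeps only presence or absence. B-, NK- and dendritic-cell counts appear nowhere except as correlates in row 1c. It is not even clear that the plots and tables listed in that row extend to them.

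If the plan is followed as written, the report will contain no planned contrast or interval for whether the belatacept regimen changes the number of antiviral T cells or of these leukocyte subsets. Sections 13.7 and 13.8 label any analysis beyond the SAP as ad hoc, so a comparison added later would lose its prespecified standing.

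**Working it through.** **1. Which rows compare arms on level.** Rows 2a, 4b, 5a and 11b fit a repeated measures ANCOVA to donor-reactive T cells, gene expression, antibodies and several viral loads. Where correlations are also wanted (2b, 5c), they sit beside a levels model (2a, 5a). Analysis 1 has two correlation rows (1a, 1c) and a binary row (1b), but no levels model.

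**2. The plan's own figure.** Section 13.2.3 illustrates a two-arm repeated measures ANCOVA with 30 per arm and 5 assessments, and gives error degrees of freedom of 58 for treatment and 238 for time and for time by treatment.
- Treatment: 60 − 2 = 58.
- Within subject, taking time as linear: 300 − 1 − 1 − 58 − 1 − 1 = 238.

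Both figures reproduce; the linear-time reading is an inference. The plan therefore regards such a model as feasible at this sample size.

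**3. What a within-arm correlation can show.** Ranks within an arm do not change if every count in that arm is halved, so the Spearman coefficient does not change either. A simulation of 4,000 runs with 30 per arm confirms this. It assumed a within-arm correlation of 0.4 in both arms and a 0.74 SD shift in level, which is about the single-visit difference detectable with 80% power at two-sided 0.05.
- Mean Spearman coefficient: 0.37 in each arm.
- Test of the two coefficients against each other: significant in 5.0% of runs, the null rate.
- t-test on levels: significant in 81% of runs.

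**4. Power of a levels model.** The plan gives no effect size, correlation or prevalence for these counts, so those are assumptions: difference 0.5 SD on the log scale, equal correlation ρ between visits, 30 complete subjects per arm, two-sided 0.05. The visits are the cytokine-staining visits in Appendices 1 and 2: pre-transplant, then weeks 28, 36 and 52.

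Mean of three visits, adjusted for the pre-transplant value:
- Residual variance = (1 + 2ρ)/3 − ρ². At ρ = 0.5: 0.667 − 0.25 = 0.417.
- Noncentrality = 0.5/√0.417 × √(30/2) = 3.00, giving about 84% power.
- At ρ = 0.3: variance 0.443, noncentrality 2.91, about 82%. At ρ = 0.7: variance 0.31, noncentrality 3.48, about 93%.

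Week 52 alone, adjusted, at ρ = 0.5:
- Residual variance = 1 − 0.25 = 0.75; noncentrality = 0.5/√0.75 × √15 = 2.24, giving about 59% power.

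**5. Power of the present/absent route.** The same counts (ρ = 0.5, shift 0.5 SD) were dichotomised at a threshold set by control-arm prevalence. The arms were compared on each subject's proportion of positive visits over the same three visits.

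| Control prevalence | Power, three visits |
|---|---|
| 50% | about 53% |
| 90% | about 41% |
| 95% | about 31% |
| 99% | about 9% |

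Both routes use three visits, but only the levels model adjusts for the pre-transplant value.

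**The case against.** A reader might infer that the arms are never compared on these cells. The documents do not support that. Rows 1a and 1c also list plots by treatment and time and summary tables, which display counts by arm, and row 1b is a between-arm test of virus-specific T cells. What stands is narrower: there is no planned contrast, interval or test of the counts.

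A reader might also infer that the protective-immunity objective goes untested. It does not. Row 11a tests treatment differences in the prevalence of six viruses, row 11b models several viral loads, and Table 9 compares the incidence of specific infectious diseases.

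A third tempting step is that EBV-specific T cells will be present in almost everyone because EBV-seronegative recipients are excluded, which would leave row 1b nothing to detect. The exclusion is an antibody criterion, every subject receives Thymoglobulin, and no prevalence is given. CMV-seronegative recipients can be enrolled (Section 8.4.1), so presence or absence may be informative for CMV.

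In the plan's defence, Section 13.2.3 states a general intent to test treatment effects, Table 10 is captioned a summary, and row 1a matches Section 12.1.1, which says the counts will be correlated with virus detection. A general intent, however, names no model, covariate or visit for these counts. The sample-size footnote does not explain the gap either, because row 2a carries the same footnote. Finally, Appendix 4 collects no staining sample after study therapy stops, so fewer than 30 per arm is likely and the power figures are optimistic.

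**Conclusion.** The concern holds as a specification gap for two listed mechanistic endpoints. It is clearest for B-, NK- and dendritic-cell counts, which lack even a prevalence test. This goes beyond missing detail, because the correlation method named for analysis 1 cannot respond to a difference in cell numbers. The primary endpoint and the clinical secondary endpoints are unaffected.

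That the gap exists rests on the text of Table 10 alone. Its size is illustrative: about 84% power (59% at week 52 alone) against 53% down to 9%, under the assumed difference, correlation, prevalences and complete data.

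**What to change.** Add to analysis 1 the repeated measures ANCOVA of row 2a, and add a row applying it to the leukocyte-subset counts. Include arm, visit, arm-by-visit and the pre-transplant value as covariate. Work on a log scale with a stated rule for zero or undetectable counts. Report the belatacept-to-tacrolimus ratio with a 95% confidence interval, overall and at week 52, labelled exploratory and subject to the existing footnote on adequate sample size. Keep rows 1a, 1b and 1c as supporting analyses.

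The cost is revised SAP wording before database lock and some extra model runs. No new samples, visits or subjects are needed. The downside is more exploratory comparisons across viruses and cell subsets, which is a reason to present estimates with intervals and not to lean on individual p-values.
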